**Equation 1**

$$E(Y_{ij}) = a_0 + b_{0j} + (a_1 + b_{1j})T_{ij}$$

Where  $a_0$  is the fixed effect term for the common intercept (across all patients),  $b_{0j}$  is the term for the random intercept of patient  $j$  and follows a Normal distribution,  $a_1$  is the fixed effect term for the common slope (across all patients) and  $b_{1j}$  is the term for the random slope of patient  $j$  and follows a Normal distribution.  $T_{ij}$  represents the time (in years) in the phase for patient  $j$  and time  $i$ . For a given patient, the random slope quantifies the difference between the observed eGFR slope of the patient and the population-averaged (common) eGFR slope. Therefore the combination of  $a_1 + b_{1j}$  represents the eGFR slope for each patient, and will be the primary quantity of interest in this analysis. The primary analysis will come from an unadjusted model as shown above. An autoregressive covariance structure will be used in this model in the first instance, however other covariance structures may be used, especially in the case of model non-convergence. If an autoregressive covariance structure results in non-convergence, then a compound symmetry structure will be tried. In the case that neither of these covariance structures results in convergence, other structures may be tried and the final choice of covariance structure will be detailed in the output. Note that the eGFR slope resulting from Equation 1 is expected to be negative as eGFR is expected to decline over time.

[figure not shown]
The primary analysis used to evaluate homogeneity of the slopes will be a shift table of the shift in number of patients with categories of estimated eGFR slopes of  $> -1$ ,  $> -3$  to  $-1$  (slow progression) and  $\leq -3$  mL/min/1.73m^2/year (fast progression) from the retrospective phase to the prospective phase. This analysis will be presented overall and for the DKD and non-DKD populations. Percentages will be based on the number of patients within each category in the retrospective phase. This analysis will

[figure not shown]
be performed once using prospective eGFR measurements from Mitra® samples and once using prospective eGFR measurements from venous blood samples.

[figure not shown]
Summary statistics (mean, SD, min, median, max) of the estimated eGFR slopes will be presented by phase, for the overall population and for the DKD and non-DKD populations, and this analysis will be performed once using prospective eGFR measurements from Mitra® samples and once using prospective eGFR measurements from venous blood samples.

To aid in assessing the reliability of the slope estimation, the residual variance (i.e. mean squared error) of the slope estimates will also be presented for both the retrospective and prospective slopes, and this residual variance will be estimated from the linear random slope model in [Equation 1](#).

A by-patient listing of the primary outcome data will be provided including patient identifier, site, country, age, sex, race, patient population (DKD/non-DKD), phase of measurement (retrospective/prospective), visit, date of baseline, sample collection/assessment day, indicator of whether sample was taken and reason not done (for prospective eGFR only), name of formula used to calculate eGFR, eGFR measurement, and indication of whether paper diary was reviewed (at clinic visits in prospective phase only), and data source (Mitra®/venous blood) for prospective phase. Note that the assessment day will be calculated relative to baseline. Data from all visits (including unscheduled visits) will be listed, and data collected 4 weeks before AKI and up to 8 weeks after the AKI (which were excluded from the analysis) will be listed and marked with [AKI] in the listing. Data excluded from the primary analysis due to changes in background therapy will be marked with [BAC] in the listing.

## 4.11 Safety Evaluation

### 4.11.1 Adverse Events

Adverse events will be coded using the MedDRA version 24.0 or higher. Per the CTP, only AEs related to study procedure will be collected for this trial, and thus only AEs related to study procedure will be analyzed. All adverse event summaries will be done on the FAS. Analyses of AEs will be limited to on-study AEs occurring between baseline and the end of study visit (inclusive) that are associated with a trial procedure. All analyses of AEs will be based on the number of patients with AEs and not on the number of AEs. Listings will include all AEs. Missing or incomplete AE start dates will be imputed according to the rules specified in section 5.2. The listings will present original (non-imputed) dates.

For each patient and each adverse event, the worst severity recorded will be attributed and used in summaries of severity. Similarly, the worst causality (most related to treatment) will be attributed and used in summaries of causality. If severity or causality is missing, a conservative approach for AE assessment (taking into account the worst case) will be followed.

An overall summary of adverse events will present the number and percentage of patients with:

- Any adverse event
- Any severe AE
- Any AE leading to discontinuation of study
- Any AE causally related to study procedure
- Any serious AE, including breakdown of type of serious AE (death / life threatening / disability or permanent damage / hospitalization (initial or prolonged) / congenital anomaly or birth defect / other serious (important medical events))
- Any AE leading to death.

Percentages will be based on the number of patients in the FAS.

Additionally, the number and percentage of patients with the following adverse event types will be summarized by primary SOC and PT:

- Any AEs
- AEs by maximum severity (mild/moderate/severe)
- AEs by causal relation to study procedure (related/not related)
- Serious AEs.

Patients with multiple AEs within the same SOC and/or PT are counted once per SOC and/or PT. The summaries will be sorted alphabetically by SOC, and then by descending frequency of PT (within SOC). Percentages will be based on the number of patients in the FAS.

A by-patient listing of all collected adverse events will be presented. This listing will include: site, country, patient identifier, patient population, age, sex, race, adverse event (SOC, PT, and verbatim term), start and stop day of AE, duration of AE (only when both the start and end dates of the AE are not imputed), outcome, severity, whether therapy required, causal relation to study procedures, seriousness, and whether AE led to discontinuation of study.

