1.4.2 Risks

During this study, 1 venous blood sample for serum creatinine (5 mL) will be collected at screening, and 3 venous blood samples for serum creatinine (5 mL), chemistry (5 mL), and hematology (2 mL) will be collected during site visits at baseline, and Week 12, Week 24, Week 36 and Week 48 (end of study). 2 tubes (5 mL and 2 mL) are used for assessing the safety parameters (chemistry and hematology) and 1 tube (5 mL) for serum creatinine. No office/hospital visits beyond those will be required. Additional blood collection by finger prick (2 x 10 microL per time point) will be conducted on a biweekly basis for the first 12 weeks and every 4 weeks thereafter at home (until Week 48) using the Mitra[®] micro sampling device*. There is minimal risk posed to patients with the use of the Mitra[®] device sampling. Most CKD patients are expected to provide venous blood samples for eGFR assessment at least every 3 – 6 months as a part of clinical practice. Hence, the blood collection planned in this study will be associated with a minimal risk for patients beyond what they would be exposed to in routine clinical practice.

* The Mitra[®] Microsampling Device is CE-certified under the European Directive on In Vitro Diagnostic Medical Devices (Council Directive 98/79/EC) and was registered at the

U.S. Food and Drug Administration (FDA) as a Class 1 Medical Device. A method for the measurement of creatinine in human capillary blood using LC-MS/MS (including extraction of the sample from the inert porous plastic tip of the Mitra® device and stability for up to three months) has been established following the 2018 FDA Guidance on Bioanalytical Method Validation.

Sampling with the Mitra® Microsampling Device is straightforward: after performing a finger prick with the supplied lancet the device is placed adjacent to the forming blood drop and approximately 10 microL of blood is absorbed by the porous tip of the device. This is done for both tips in the cartridge, which is then closed and sent away for analysis. The procedure can be easily performed by the patient or a caregiver.

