5.2.6.2 Adverse Event Collection and Reporting

This interventional clinical trial does not involve administration of any study medication. Therefore, the following applies:

The following must be collected and documented on the appropriate CRF(s) by the investigator: from signing the informed consent onwards until the End of trial visit - all AEs associated with trial procedure (non-serious and serious). AEs have to be followed up until they are resolved.

In addition, the investigator should report to BI all adverse events related to any BI products as determined by the investigator via established channels of reporting in the country e.g. local forms or call center number. This includes any drug exposure during pregnancy with and without adverse events.

[figure not shown]

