7.2.5 Safety analyses

The safety analyses are limited to the “AE” related to study procedures. Adverse events will be coded using the Medical Dictionary for Drug Regulatory Activities (MedDRA). Standard BI summary tables and listings will be produced.

All treated patients will be included in the safety analysis. In general, safety analyses will be descriptive in nature and will be based on BI standards. No hypothesis testing is planned.

Frequency, severity, and causal relationship of adverse events will be tabulated by system organ class and preferred term after coding according to the current version of (MedDRA) at database lock.

Laboratory data will be analysed both quantitatively as well as qualitatively. The latter will be done via comparison of laboratory data to their reference ranges. Values outside the reference range as well as values defined as clinically relevant will be summarised. Treatment groups will be compared descriptively with regard to distribution parameters as well as with regard to frequency and percentage of patients with abnormal values or clinically relevant abnormal values.

Further details will be provided in the TSAP.

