#### 4.6 Analysis Sets

The enrolled set includes all patients for whom main informed consent was obtained.

All analyses will be based on the FAS, which will consist of all patients entered into the 48-week prospective phase of the study who have at least one post-baseline assessment. Since this is a non-randomized study with no trial drug administration, there is no need for a separate Safety Analysis Set, and both safety and non-safety summaries will be done on the FAS.

Upon database release, protocol deviation and analysis set outputs will be produced and will be sent to Boehringer Ingelheim for review. An analysis set classification meeting will be arranged if applicable to discuss the outputs and to decide which patients and/or patient data will be excluded from certain analyses. Decisions made regarding the exclusion of patients and/or patient data from analyses will be made prior to the final analysis, and will be documented and approved by Boehringer Ingelheim.

A summary of the number and percentage of patients in each analysis set will be presented for the enrolled set, with denominators based on the number of patients who were enrolled. The number of patients not included in the FAS with the reason for exclusion will also be presented, with denominators based on the number of patients who were enrolled.

A by-patient listing of analysis set details will be presented for all enrolled patients, including the patient identifier, patient population, site, country and indication of inclusion/exclusion from each analysis set, and reason for exclusion (from FAS only). If patient data has been partially excluded from an analysis set, details of the data and visit that has been excluded will appear on this listing.

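### Adverse event summaries start at baseline and use the FAS, so procedure-related events at screening, and any event in a patient with no post-baseline assessment, are in no AE table

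*SAP*

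**What the plan says.** **Collection.** Protocol 5.2.6.2 requires events to be recorded "from signing the informed consent onwards until the End of trial visit - all AEs associated with trial procedure (non-serious and serious"). The flow chart marks AE collection at the screening visit as well as at the clinic visits from baseline on.

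**Procedures.** Protocol 1.4.2 places the first one before baseline: "1 venous blood sample for serum creatinine (5 mL) will be collected at screening". At baseline and Weeks 12, 24, 36 and 48, "3 venous blood samples for serum creatinine (5 mL), chemistry (5 mL), and hematology (2 mL) will be collected during site visits". Finger-prick (Mitra) sampling starts at baseline.

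**Summaries.** SAP 4.11.1 states: "Analyses of AEs will be limited to on-study AEs occurring between baseline and the end of study visit (inclusive"). It adds: "All adverse event summaries will be done on the FAS". SAP 4.6 defines the FAS as "all patients entered into the 48-week prospective phase of the study who have at least one post-baseline assessment". Citing the non-randomised design and the absence of a trial drug, it concludes that "there is no need for a separate Safety Analysis Set, and both safety and non-safety summaries will be done on the FAS".

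**Protocol safety population.** Protocol 7.2.5 says: "All treated patients will be included in the safety analysis". It leaves further detail to the SAP.

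**Declared changes.** SAP 4.13 lists departures from the protocol. Neither the narrower AE window nor the FAS restriction is among them.

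**The concern.** The SAP's reason for having no safety set is that there is no trial drug. That reasoning overlooks where the risk lies. By SAP 4.11.1 itself, only AEs related to study procedures are analysed, so the procedures are what the AE tables are meant to describe. An analysis set for that purpose should include everyone who had a procedure. The FAS instead includes those who had procedures and then stayed long enough to provide a later assessment.

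The patient most likely to be missed is one the tables should show: someone who has a sampling-related event at screening or baseline and stops because of it. That patient is in neither the numerator nor the denominator of the AE overview, including its row for events leading to discontinuation. The tables also describe a shorter period than the one over which the protocol collects events, and nothing in the SAP alerts the reader to this.

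**Working it through.** No sample size, power or error-rate figure bears on this point. The check is a comparison of the rules, a count of procedures, and a short argument about the direction of bias.

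**1. Where each kind of event ends up**

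| Situation | Collected (Protocol 5.2.6.2) | In an AE table (SAP 4.11.1, 4.6) | In the AE listing (SAP 4.11.1) | In disposition (SAP 4.5.1) |
|---|---|---|---|---|
| Event at screening, patient later in the FAS | Yes | No | Yes | Not applicable |
| Event at screening, patient never enters | Yes | No | Yes | Reason for not entering |
| Event on or after baseline, patient stops with no post-baseline assessment | Yes | No | Yes | Reason for discontinuation |
| Event on or after baseline, patient in the FAS | Yes | Yes | Yes | If discontinued |

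The date rules in SAP 5.2 agree with this. An event whose possible onset interval ends before baseline, or whose patient has no baseline date, is classed as not on-study. One narrow exception exists: an incomplete onset date whose interval spans baseline is set to baseline and counted as on-study.

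**2. Two discontinuation figures on different bases.** SAP 4.5.1 bases discontinuation percentages on patients who entered, meaning those who passed screening and completed the baseline assessment. The AE overview bases its discontinuation row on the FAS. A patient who enters and stops because of a baseline sampling event, with nothing recorded later, is counted in the first and absent from the second.

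**3. How much of the procedure schedule lies before baseline.** Inputs are from Protocol 1.4.2 and the flow chart, for a patient who completes the trial, ignoring repeat and unscheduled samples.

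- Venous occasions: 1 at screening + 5 from baseline = 6. Screening share 1/6 = 16.7%.
- Venous samples: 1 + 5 × 3 = 16. Share 1/16 = 6.3%.
- Venous volume: 5 + 5 × (5 + 5 + 2) = 65 mL. Share 5/65 = 7.7%.
- All sampling dates, following the text (every 2 weeks to Week 12, then every 4 weeks to Week 48): baseline 1 + Weeks 2 to 12 6 + Weeks 16 to 48 9 = 16 Mitra dates, and the five venous dates from baseline fall on these. With screening, 17. Share 1/17 = 5.9%.
- All sampling dates, following the flow chart's visit columns: Visits 2 to 14 = 13, plus screening = 14. Share 1/14 = 7.1%.

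**4. What a patient without a post-baseline assessment has undergone.** Up to 2 venous occasions, 1 + 3 = 4 venous samples and 5 + 12 = 17 mL, plus the baseline finger prick and, if the patient consented to biobanking, about 20 mL more. None of this patient's events reaches an AE table.

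**5. Direction of bias from the FAS restriction.** Let the FAS have n patients, a of them with an event. Let m entered patients lack a post-baseline assessment, k of them with an event. The table reports a/n; over all entered patients the figure would be (a + k)/(n + m). The reported figure is too low only if k/m > a/n. If the excluded patients stopped because of sampling events, k/m is high and the tables understate. If they are mostly event-free patients with one or two sampling visits, k/m is low and the tables overstate. The documents give none of a, k, n or m.

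**The case against.** **Nothing is lost from the report.** SAP 4.11.1 lists every collected event, with seriousness, relation to procedure and whether it led to discontinuation. SAP 4.5.1 gives reasons for discontinuation over all who entered, and reasons for not entering. This stands. A reader might infer that the excluded events vanish, and they do not. But a listing has no denominator, and two tables that can give different discontinuation counts without explanation still need reconciling.

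**Collection and tabulation can differ.** Protocol 5.2.6.2 governs what is recorded, and Protocol 7.2.5 defers detail to the SAP. This also stands: the narrower window does not contradict the collection rule. The population named in Protocol 7.2.5 is a different matter. It has no clear meaning in a trial without treatment, but it carries no post-baseline condition, and the SAP neither interprets it nor declares a departure.

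**Few patients are likely to be affected.** Any one post-baseline assessment admits a patient to the FAS, and Protocol 6.2.5 asks early discontinuers who keep consent to return for an End of Trial visit with full sampling. Protocol 1.4.2 describes the added sampling risk as minimal. These points limit the size. They do not help the patient who withdraws consent or does not return.

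**Stronger readings the documents do not support.** A reader might take one sixth of the exposure to be unsummarised. That counts venous occasions only; on the other counts above the share is about 6% to 8%. A reader might apply an assumed early-loss rate to the planned 600, for example 2% to 5%, giving 12 to 30 patients. The rate has no source in the documents, and SAP 3.1.1.1 records that the trial was terminated in July 2022 without stating how many had enrolled. A reader might also conclude that AE rates are biased downward. Termination could leave recent entrants without follow-up for administrative reasons, and step 5 above shows the net effect can go either way.

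**Conclusion.** The concern holds in a limited form. Selecting the AE analysis set on continued participation after the exposure is a flaw in a trial where procedures are the only exposure, and it can hide AE-driven early stopping from the AE tables. The baseline start also removes screening events from the tables for every patient, apart from the partial-date exception. Neither restriction is declared in SAP 4.13.

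The size is unknown and probably small. That judgement rests on a single 5 mL draw being the only blood sampling scheduled before baseline, and on the End of Trial visit bringing most early discontinuers into the FAS. The documents give no AE rate, no early-loss rate and no final enrolment, so the number of affected patients cannot be calculated. The analysis is descriptive, so no inferential conclusion is at stake. What is at stake is whether the AE tables describe everyone exposed, and whether they agree with disposition.

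**What to change.** In SAP 4.6, define a safety set for AE summaries: all consented patients who had at least one trial procedure, with no post-baseline requirement. It is a subset of the existing enrolled set.

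In SAP 4.11.1, report two columns:

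- Consent to baseline, with its own denominator: all patients in the safety set. Keeping this separate prevents screen failures, who have had only the screening draw, from diluting the on-study percentages. The not-on-study class in SAP 5.2 already identifies these events.
- Baseline to end of study, with all patients who entered as the denominator. This aligns the discontinuation row with the disposition table.

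Keep the FAS for the slope analyses. Record the change in SAP 4.13, and state there how the new set relates to the population named in Protocol 7.2.5.

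The cost is SAP wording and a re-run of the AE tables. No new data are needed, because the events are already collected and listed.

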#### 4.11.2 Clinical Laboratory Evaluation

The analyses of laboratory data will be descriptive in nature. Analyses will be based on SI units and on standardized values for all parameters except urine albumin, urine protein, urine creatinine, UACR and PCR, which will be reported in the conventional units. Results from the central laboratory will be included in the reporting of this study for the following laboratory groups:

- Hematology
- Chemistry
- Urine Chemistry.

Laboratory parameters will be collected at the following visits, as per the CTP (for all parameters except eGFR collected at home via Mitra® micro sampling):

- Baseline (visit 2)
- Visit 5
- Visit 8
- Visit 11
- Visit 14 (end of study visit).

For eGFR collected at home via Mitra® micro sampling, these will additionally be collected at visits 3, 4, 6, 7, 9, 10, 12, 13 and will be collected bi-weekly at visits 2, 3 and 4.

For by-visit summaries, the last non-missing assessment (including repeat assessments) recorded at each visit will be summarized. In the case that there are multiple measurements taken on the same date and time, and these measurements are simultaneously the last non-missing assessment at a visit, then the mean of these measurements will be taken and this average will be used in the analysis. Unscheduled visits will not be included in the summary tables. Listings will present all visits, including unscheduled ones.

At each visit, laboratory measurements will be compared with the relevant laboratory reference ranges and categorized as abnormal (low/high) or normal:

- Low: below the lower limit of the laboratory reference range
- Normal: within the laboratory reference range (upper and lower limit included)

- High: above the upper limit of the laboratory reference range.

Descriptive summaries of the baseline, post-baseline and change from baseline in laboratory parameters will be presented by laboratory parameter and visit. Additionally, a summary of the number and percentage of patients with abnormal laboratory values will be presented by laboratory parameter and visit. Percentages will be based on the number of patients with a measurement at the visit (per parameter).

Laboratory values will be listed by patient and study time point including: patient identifier, patient population, age, sex, race, country, site visit, visit day, indication of whether assessment was performed and reason not done, laboratory parameter, result, and change from baseline. All values outside the clinical reference ranges will be flagged in the data listings. The abnormal values will be flagged with 'L' for values below the lower limit of the clinical reference range and 'H' for values above the upper limit of the clinical reference range.

